### **VII. RISKS AND DISCOMFORTS**

**VII.a. complication of procedures** none

**VII. b. Drug side effects and toxicities** none

**VII. c. Device complications/malfunctions.** The battery-operated activity monitoring device and the mini iPad are electrically safe and present minimal risk.

#### **COMMON**

**VII. d. Psychosocial (non-medical) risks.** Participants randomized into the 8-h scheduled sleep groups will be required to remain in bed attempting to sleep for 8 h following two successive night shifts. While they may feel frustrated with this if they cannot sleep, there is no long-term risk associated with this, and we anticipate that most participants will actually receive more sleep than they would typically get with ad lib sleep.

-It is possible that the participants randomized to the 8-h afternoon-evening sleep group will feel sleepy from the time they get off the night shift until the early afternoon scheduled bed time, which they may find frustrating. Due to the likelihood that participants randomized to the 8-h afternoon-evening sleep group will be awake for 24 or more hours after the first night shift in the Intervention week, they will be advised to use extra caution if they take part in any safety-sensitive activities that would put them at risk for an accident. All participants will be informed that they should use whatever countermeasures they routinely use to keep them safe (e.g., caffeine) and that they may withdraw from the study at any point that they feel the study conditions are too difficult

-There are minimal risks to participating in the Shift Worker Survey. Participants may experience some psychological discomfort responding to personal questions such as those about stress. Participants may choose not to answer any questions that they are not comfortable with. REDCap allows us to segregate identifiable information from the survey responses, and only the PI and one other study team member will have access to the identifiable information. There will be a code to link between the identifiable information and the survey data.

-There are minimal risks to participating in the virtual Focus Groups by secure videoconference. There is a small risk of feeling loss of confidentiality during focus group discussions. Participants will be asked to use an “alias” instead of their real name during focus group discussions. Audio recordings of focus group discussions will be destroyed upon completion of the study. No identifying information will be on the focus group transcript.

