The Baseline Block consists of a week during which participants work at least three consecutive 8-h night shifts. The three night shifts are preceded by a day off. All participants will be instructed to continue their normal routines, maintaining their habitual self-selected sleep-wake schedule. Sleep-wake and light exposure patterns will be recorded continuously using actigraphy, and a daily sleep e-diary will be filled in within the first hour after awakening from each main sleep episode. Performance (attention), alertness and mood will be rated three times on each night shift (just prior to their shift, on a break during their shift, and immediately after their shift). The purpose of this Baseline segment is to obtain measures of sleep duration and consolidation (to address Aim 1), alertness, mood, and performance (to address Aims 2, 2a and 2b) when working night shifts following their typical sleep routine. Immediately after the third night shift, an optional saliva sample will be taken to measure stress level (cortisol) and each participant will complete a baseline questionnaire covering questions related to fatigue, recovery, stress, and quality of life (to address Aim 2a). Participants will be given a specially configured mini iPad on which the E-diary, the performance test, alertness and mood rates, and fatigue, recovery, stress and quality of life questionnaire are programmed on.

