The Intervention Block is similar to the Baseline Block, consisting of at least three consecutive 8-h night shifts, with the participants wearing an activity monitor, maintaining a daily sleep e-diary, and rating alertness, mood and attention three times per night shift using a mini iPad provided by the investigators. At the end of the first night shift, the participant will be told about their randomization group. In the control group (Group A), participants will not be given any instructions about the timing or duration of their sleep, but will be instructed to follow their usual night shift sleep routine. In the 8-h afternoon-evening sleep intervention group (Group B), participants will be instructed to go to bed between 13:00 and 14:00 (depending on their individual commute time) and to remain in bed attempting to sleep for 8 hours (until 21:00-22:00) before the next two night shifts. In the 8-h free sleep group (Group C), participants will be instructed to remain in bed for 8 continuous hours before the next two night shifts, but will not be given any instruction regarding which 8 hours they should sleep. Immediately following the last night shift, the participant will have the option to take a saliva sample to measure their stress level (cortisol), and they will complete a follow-up questionnaire where their fatigue, recovery, stress, and quality of life will be reassessed to investigate any exploratory short-term changes resulting from the intervention schedule. After completion of the two blocks, the participant will send back the activity monitor and iPad in a prepaid secured return package by mail or an investigator will arrange to meet with the participant to retrieve the activity monitor, iPad, and cortisol sample. Within 3 months after completion of the study blocks the participant will be invited to take part in a virtual Focus Group by secure videoconferencing (via HIPAA-compliant & MGB-approved Zoom).

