### **IX. c. Outcomes monitoring.**

Ongoing study progress, including enrollment in each aspect (Field Trial, Shift Work Survey, Focus Groups), data quality/integrity, completeness, and safety issues, will be reviewed weekly by the study team. During these meetings the Principal Investigator and other members of the research team are present.

In the Field Trial, a study team member will be available to the participants at all times via telephone or text/email to answer questions, and to take reports of any accidents or injuries. The eDiary entries and performance tests will be monitored checked daily by a study team member to ensure the participant is completing them and to follow-up in cases where there are missing or potentially incorrect entries.

**IX. d. Procedures for identifying, reviewing, and reporting adverse events and unanticipated problems to the IRB and NIH.** The PI will be ultimately responsible for reviewing and reporting all adverse events and unanticipated problems to the IRB and the NIH as required. She will review the data and meet with the study team weekly to discuss any problems (anticipated or unanticipated) with the research study, as well as any adverse events. In addition to adverse events, the PI and study staff will regularly review study progress to identify unanticipated problems, and report these to the IRB and NIH as required.

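### The prolonged-wakefulness caution is addressed to Group B only, but a Group C participant who chooses the afternoon-evening slot is awake just as long; one sentence to all participants would cover this

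*Combined protocol and SAP*

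**What the plan says.** Section VII.d (Psychosocial risks) gives the reason, "Due to the likelihood that participants randomized to the 8-h afternoon-evening sleep group will be awake for 24 or more hours" after the first Intervention night shift, and then the advice: "they will be advised to use extra caution if they take part in any safety-sensitive activities". The advice is addressed to the group named in the reason, Group B. The next sentence is for everyone: "All participants will be informed that they should use whatever countermeasures they routinely use to keep them safe". It also reminds participants that they may withdraw. It does not mention long wakefulness or safety-sensitive activities. Section IX.c adds a contact route: "a study team member will be available to the participants at all times via telephone or text/email to answer questions" and to take reports of accidents or injuries.

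Under the Intervention Block in Section V, Group B is told to go to bed between 13:00 and 14:00 and stay there for 8 hours. Group A keeps its usual routine. Group C must also spend 8 continuous hours in bed, "but will not be given any instruction regarding which 8 hours they should sleep". Assignment is disclosed late: "At the end of the first night shift, the participant will be told about their randomization group". In Section VI, the Aim 2b analysis includes a rule for Group C participants who chose afternoon-evening sleep, so the plan expects that this may happen.

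**The concern.** The danger named in VII.d is long continuous wakefulness. Hours awake depend on when a person last woke and when they go to bed. Assignment fixes the bedtime in Group B only. Because it is disclosed after the first Intervention shift, it cannot have influenced the wake time before that shift. A Group C participant who meets the study's 8-hour requirement in the afternoon slot can therefore have the same exposure as Group B without being addressed by the caution.

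What is at stake is participant safety. The background section links night work to accidents at work and on the commute, and says that the decline with time awake is amplified during the biological night. Sample size, power and the outcome analyses are not involved.

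**Working it through.** **Inputs from the protocol**
- Group B bedtime 13:00-14:00, with 8 h in bed (Section V, Intervention Block).
- 8-h night shifts (Sections III.a and V).
- Waking 1-2 h before the next shift on the afternoon-evening schedule (Section II).
- Night workers typically get up 8 h or more before their shift (Section II).
- Commute under 1 h (Section III.a).

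The protocol gives no shift clock times and no wake times for the day of the first Intervention shift. Those used below are assumptions.

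**Reading of the 24-hour figure.** It cannot be counted from the end of the shift, because bedtime comes only 6-7 h after that (step 2). It must mean total time awake by the first scheduled bedtime.

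**1. The plan's own figure, Group B.** Hours awake = 24 + bedtime - last wake time.

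| Last woke | Bed 13:00 | Bed 14:00 |
|---|---|---|
| 07:00 | 24 + 13 - 7 = 30 h | 31 h |
| 10:00 | 27 h | 28 h |
| 13:00 | 24 h | 25 h |
| 14:00 | 23 h | 24 h |
| 16:00 | 21 h | 22 h |

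So 24 h or more is reached when the person last woke at or before the clock hour of the bedtime. A nap ending at 21:00 before the shift would bring the total down to 16-17 h. The plan's statement of likelihood is reproduced for a wake time up to 13:00 or 14:00.

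**2. The same in terms of pre-shift wakefulness.** Let p be the hours awake before the shift.
- Bed 13:00: rise 21:00, shift start 22:00 or 23:00, end 06:00 or 07:00. From shift end to bed is 7 or 6 h.
- Bed 14:00: rise 22:00, start 23:00 or 24:00, end 07:00 or 08:00. From shift end to bed is again 7 or 6 h.
- Total = p + 8 + (6 to 7) = p + 14 to 15 h.
- p = 8 gives 22-23 h; p = 9 gives 23-24 h; p = 10 gives 24-25 h.

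**3. Group C in the afternoon slot.** For an assumed 23:00-07:00 shift and a commute of 0-1 h, the earliest bedtime is 07:00-08:00. The latest is 23:00 - 8 h - (0 to 1 h) = 14:00-15:00. A bedtime of 13:00-14:00 is therefore open to Group C, and the formulas in steps 1 and 2 apply unchanged. At the same wake time and bedtime, the hours awake equal those of Group B.

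**4. Morning bedtime, any group.** With bed 1 h after shift end, total = p + 8 + 1 = p + 9 h. p = 8 gives 17 h and p = 10 gives 19 h. Reaching 24 h needs p = 15, which is a wake time of 08:00 before a 23:00 shift.

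**5. Is an early wake time documented?** Only indirectly. For the Baseline Block: "The three night shifts are preceded by a day off". For the other: "The Intervention Block is similar to the Baseline Block". Section I.a describes night sleep and daytime activity on days off. Together these make a morning wake before the first shift plausible. They do not establish it.

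**The case against.** The strongest reply is that the stated reason is not 24 hours awake in the abstract. It is the likelihood of this in the group whose bedtime the study delays. On that reading, VII.d warns about the risk that the study creates, and Groups A and C carry only what they choose or already do. Section I.a says that the typical night worker goes to bed in the morning after work, and step 4 then gives 17 h at 8 h of prior wakefulness. All participants are told to use their usual countermeasures and may withdraw, and staff can be reached at all times. Consent is obtained before the study begins (Section IV.b), so a caution printed in the consent form would reach every participant whatever their later group.

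Most of this stands. Targeting Group B is defensible, and the general safeguards are real. What remains is narrow. Group C's 8 hours in bed are also a study requirement, and Section VIII.a pays for keeping the assigned sleep episode. A participant who meets that requirement in the afternoon has Group B's hours awake, and neither the all-participant sentence nor the contact line carries the caution.

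A reader might infer more: that limiting the caution to Group B is a mistake, that Group A is similarly exposed, or that a known share of participants is left unwarned. The documents support none of these. Group A's route depends on undocumented early waking, no share of Group C is given for the afternoon slot, and the consent text cannot be checked.

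**Conclusion.** This is a minor improvement to safety wording, not an error in the plan. A Group C participant in the 13:00-14:00 slot reaches 24 h awake under the same condition as Group B: having last woken at or before that clock hour, which is 9-10 h or more before the shift. At 8 h the total falls just short, at 22-23 h. Long wakefulness in Group A, or with a morning bedtime, is possible but less likely, and the study does not impose it.

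The equality between Groups B and C needs only the same wake time and bedtime. The clock-time results rest on the 1-2 h gap before the shift and on no nap being taken. How many people are affected cannot be estimated from the documents. Confidence is medium, mainly because the consent text may already close the gap. No effect on any comparison between groups is claimed.

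**What to change.** Keep the Group B advice as written. Add one sentence to VII.d, and to the consent text if it is not already there. It should tell all Field Trial participants, in identical words and before the Baseline block, to use extra caution in safety-sensitive activities whenever they have been awake for about 24 hours or will have been by their next bedtime. The sentence need not mention afternoon bedtimes; if it does, the wording should be neutral, so that Group C's choice is not steered.

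Do not add a separate message for Group A or C at disclosure. The existing Group B advice then remains the only difference between groups in what they are told about this risk.

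The cost is one sentence and a slight prompt about prolonged wakefulness that is the same in every group. Schedule, sample and analysis do not change.

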## **VII. e. Radiation risks** none

## **VIII. POTENTIAL BENEFITS**

### **VIII. a. Potential Benefits to participating individuals**

Taking part in any of the proposed study activities are unlikely to benefit any individual participant.

Participants who take part in the Field Trial will be compensated as follows: \$10.00 per day for wearing the wrist activity-light recorder and maintaining the daily sleep e-Diary for the Baseline week and the Intervention week (total up to \$140.00); \$15.00 per day for completing the thrice-daily (before start of shift, during mid-shift break, at end of shift) subjective alertness and mood assessments and the performance assessment on the three successive night shifts in the Baseline week and the Intervention week (total \$90.00); \$10.00 per day for collecting the optional saliva sample after the third night shift in the Baseline week and the Intervention week (total \$20); \$50.00 per day for maintaining the assigned scheduled sleep episode following the two night shifts during the Intervention week (total \$100.00); and a \$150.00 study completion bonus for completing all the study procedures (not including the optional saliva samples). If all procedures are completed, a participant will receive up to \$480 (\$500 if both optional saliva samples are collected) by check.

Participants who complete the Shift Worker Survey and Health Care Worker screening survey for the Field Trial will receive a \$15 gift card. These will be provided through an online vendor such as Tangocard.com. Upon completion of the questionnaire, the participant will be asked to choose the gift card they would like, and an electronic gift card will be sent to their email address, a method we have used successfully for other studies.

Participants who take part in a virtual Focus Group will receive \$75.00 by check for taking part in the focus group.

### **VIII. b. Potential Benefits to society**

Night and rotating shift work can result in shortened and disrupted sleeping during the daytime, leading to sleepiness on the following night shift and an increased risk of accidents both at work and while commuting home. While the sleep intervention we will test may appear so simplistic as to not merit testing, the facts are that most shift workers do not devote sufficient time for sleep. A rigorous field study testing whether remaining in bed attempting to sleep will result in longer and higher quality sleep could serve as important evidence that a 2018-P-002341 *Detailed Protocol v5 2020\_09\_25*

behavioural strategy could improve sleep quality for many shift workers. Evidence supportive of this strategy will also provide guidance for individual shift workers, employee health and wellness programs, and fatigue management plans. A practical nonpharmacologic treatment for improving the sleep of older night workers holds great potential in providing a specific and sustainable countermeasure that would enhance alertness, mood, safety, and general well-being and may result in longer-term health impacts.

## **IX. MONITORING AND QUALITY ASSURANCE**

### **IX. a. Independent monitoring of source data.**

Data quality will be monitored by the PI and the study personnel. All data from the Field Trial (questionnaires, activity recordings, sleep diaries, performance, mood and alertness assessments and saliva samples) will be collected and recorded using a study code rather than individually-identifying information. The Shift Work Survey will be collected using REDCap. Personal identifying information will be deleted from the Focus Group transcripts before analyses.

### **IX. b. Safety monitoring.**

The PI, with assistance from the study personnel, will be responsible for safety monitoring for participants in the Field Trial and the Focus Groups.

### **IX. c. Outcomes monitoring.**

Ongoing study progress, including enrollment in each aspect (Field Trial, Shift Work Survey, Focus Groups), data quality/integrity, completeness, and safety issues, will be reviewed weekly by the study team. During these meetings the Principal Investigator and other members of the research team are present.

In the Field Trial, a study team member will be available to the participants at all times via telephone or text/email to answer questions, and to take reports of any accidents or injuries. The eDiary entries and performance tests will be monitored checked daily by a study team member to ensure the participant is completing them and to follow-up in cases where there are missing or potentially incorrect entries.

**IX. d. Procedures for identifying, reviewing, and reporting adverse events and unanticipated problems to the IRB and NIH.** The PI will be ultimately responsible for reviewing and reporting all adverse events and unanticipated problems to the IRB and the NIH as required. She will review the data and meet with the study team weekly to discuss any problems (anticipated or unanticipated) with the research study, as well as any adverse events. In addition to adverse events, the PI and study staff will regularly review study progress to identify unanticipated problems, and report these to the IRB and NIH as required.

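### The protocol describes only participant-initiated reporting of accidents and injuries and no harms table by group, so under-recording and differential reporting cannot be excluded

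*Combined protocol and SAP*

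**What the plan says.** Section IX.c makes a study team member available to Field Trial participants at all times, to answer questions and "to take reports of any accidents or injuries". The same section has staff check e-diary entries and performance tests daily, with a stated purpose of completeness and correctness: "to ensure the participant is completing them and to follow-up in cases where there are missing or potentially incorrect entries". It also puts safety issues among the topics of the weekly team review.

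Section IX.b says that the principal investigator, assisted by study personnel, "will be responsible for safety monitoring for participants in the Field Trial and the Focus Groups", and gives no procedure. Section IX.d has the word identifying in its heading, but what follows concerns review and reporting: "She will review the data and meet with the study team weekly to discuss any problems". It gives no method of eliciting events.

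Section VII.d refers to the likelihood that participants in the afternoon-evening group "will be awake for 24 or more hours after the first night shift in the Intervention week", and says that "they will be advised to use extra caution if they take part in any safety-sensitive activities". The reminder about usual countermeasures, and the right to withdraw, go to everyone.

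Under Section V, participants learn their group at the end of the first night shift of the Intervention Block. In both blocks "a daily sleep e-diary will be filled in within the first hour after awakening from each main sleep episode" or its equivalent applies to all groups. The end-of-block questionnaire covers quality of life, stress, fatigue and recovery. Section VI plans no analysis or table of accidents, injuries or other harms.

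**The concern.** The protocol anticipates a specific hazard in one arm, namely a long stretch of wakefulness in people leaving a night shift. Section VIII.b recognises that night work raises accident risk on the job and on the journey home. The events most relevant to that hazard are falling asleep at the wheel, a near miss, or an injury at work or at home. Participants may not think to volunteer these, and Section I.a itself notes that people short of sleep do not recognise how impaired they are.

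Reporting is also open to influence by group. Participants are unblinded when the exposure begins, and only Group B receives the extra caution. If events are not asked about in the same way in every arm, even a descriptive account of what happened in each arm is hard to interpret. Section VIII.b expects supportive results to guide individual workers and employers' fatigue management plans, so readers will want that account.

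**Working it through.** **1. How an event could reach the record, by the documents.**

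| Source | Section | Described as asking about accidents or injuries? |
|---|---|---|
| Phone, text or email line | IX.c | Takes reports; the participant initiates |
| Daily e-diary | V | No such item described; the item list is not given |
| Daily staff check of diary and tests | IX.c | No; for missing or doubtful entries |
| Alertness, attention and mood tests | V | No |
| End-of-block questionnaire | V | No |
| Weekly review by the principal investigator | IX.d | Reviews events; no method of eliciting them |
| Harms table by group | VI | None planned |

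**2. Could reporting differ by group?** The route is the same in all three arms. What differs is knowledge of assignment and the caution given to Group B. The caution could prompt Group B to report more. Equally, participants told that they should take care may be reluctant to report a lapse. The documents do not settle the direction.

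**3. The plan's arm size.** Section VI.d gives 25 per group for a total sleep time difference of 78 min, SD 84.4, alpha 0.05 and power 0.9 (printed as beta). With a two-sided normal approximation, n = 2 × (1.960 + 1.282)² × 84.4² / 78² = 24.6, rounded up to 25, with power 0.904. The t-test gives 0.893. The figure reproduces. It matters here only because it fixes the arm size for any harms summary.

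**4. Effect of incomplete reporting (assumed values).** Let p be the true risk per participant and r the share of events reported. The chance of recording at least one event in an arm of 25 is 1 − (1 − p·r)^25. At p = 0.04, full reporting gives 1 − 0.96^25 = 0.64 and half reporting gives 1 − 0.98^25 = 0.40.

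| Assumed risk p | r = 1 | r = 0.5 | r = 0.25 |
|---|---|---|---|
| 2% | 0.40 | 0.22 | 0.12 |
| 4% | 0.64 | 0.40 | 0.22 |
| 8% | 0.88 | 0.64 | 0.40 |
| 12% | 0.96 | 0.79 | 0.53 |

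**5. What complete capture could show.** With zero events in n participants, the one-sided 95% upper bound is 1 − 0.05^(1/n). For n = 25 this is 11.3%. For n = 33 (100 completers over three groups) it is 8.7%. The two-sided exact upper limit for n = 25 is 1 − 0.025^(1/25) = 13.7%.

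**6. Could the arms be compared?** Fisher exact power at 25 per arm, two-sided 0.05, with full capture is 0.8% for 2% vs 8%, 3.5% for 4% vs 12%, and 23% for 4% vs 20%. For 80% power the normal approximation requires about 206, 180 and 64 per arm.

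**The case against.** Four points on the other side carry weight.

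First, a reader might infer that events are recorded solely when a participant calls. The documents do not say so. It is the only route described, but daily checking leads to contact over missing entries, and the principal investigator reviews data weekly. An event could surface through either. The e-diary's items are not listed, so the most one can say is that no such item is described. The consent form may also carry reporting instructions and is not counted against the plan.

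Second, a reader might infer that harms will be under-recorded and the arms not comparable. Nothing in the documents shows this. The stated route is identical across arms, no reporting rate is given, and any difference could run either way. One could divide the 11.3% bound by an assumed capture share (0.113/0.5 = 22.6%; 0.113/0.25 = 45.2%), but those shares are assumptions and the results are not evidence of impact.

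Third, sample size and a two-sleep exposure limit any safety statement far more than the reporting route does, as steps 5 and 6 show. Accidents are not a stated aim or outcome, and the reference to fewer errors and injuries in Section I.a is conditional background. This stands, and it limits the gain to a sound descriptive record.

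Fourth, a solicited item is still self-report by people who know their group, and it would not necessarily bring an urgent event to attention sooner than a line that is always open. This also stands. What the item would change is that everyone is asked the same question at the same points.

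**Conclusion.** The point holds as a gap in the described method. Reporting of accidents and injuries is passive as written, and no tabulation by group is planned. The protocol nonetheless foresees a likelihood of very long wakefulness in Group B, and participants know their assignment. Under-recording and differential reporting cannot be excluded; neither is demonstrated, and the direction of any difference is unknown.

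The size cannot be estimated from the documents. The figures in step 4 rest on assumed risks of 2% to 12% and assumed reporting shares. The bounds in step 5 rest only on the arm size and on complete capture. No stated aim, estimate or planned analysis changes. The case for acting is that a better method is available through an instrument that every participant already completes and staff already check.

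**What to change.** Add one solicited yes/no item, with brief detail, to the daily e-diary, worded identically in all three groups and both blocks. It should ask about any accident, injury, near miss, or falling or nearly falling asleep while driving since the last entry.

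- Define each term in the protocol, and state which positive answers are handled as adverse events under Section IX.d.
- Check that at least one diary entry in each block follows the journey home from the third shift.
- Keep the phone, text and email route for immediate reports.
- Add to Section VI a table by randomised group, with exact confidence intervals and the Baseline Block as within-person reference. Label it descriptive, with no test between groups and no claim of safety from an absence of events.

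The cost is reprogramming the e-diary on the study iPads, an IRB amendment, under a minute a day for participants, slightly more entries for staff to review, and one table. The answers would remain unblinded self-report. If participants have already completed the study without the item, report them separately, because their events were collected differently.
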